PI	Principal Investigator
PIS	Participant Information Sheet
PSWQ	Penn State Worry Questionnaire
QA	Quality Assurance
QC	Quality Control
REC	Research Ethics Committee
SAE	Serious Adverse Event
SDV	Source Data Verification
SOP	Standard Operating Procedure
TMF	Trial Master File
YSD	Yolk Sac

STUDY SUMMARY

STUDY OVERVIEW	
Full title	The Psychological Effects of Miscarriage Prediction Score: A Prospective Study
Objectives	Primary: Assess psychological effects of the miscarriage prediction model. Secondary: Evaluate patient acceptability.
Type of trial	A randomised, single-site trial in pregnant women with ongoing intrauterine pregnancies <12 weeks.
Trial design and methods	Prospective, non-blinded RCT at a single centre. HADS and PSWQ used to assess psychological impact at baseline and day 7.
Health condition(s) or problem(s) studied	Threatened miscarriage, psychological impact in early pregnancy.
Target sample size	372 participants (186 per arm, adjusted for consent/dropout).
Trial duration per participant:	7 days (from consent to follow-up psychological questionnaire).
Main inclusion/exclusion criteria:	Inclusion: Pregnant women >16 years with ongoing singleton intrauterine pregnancy <12 weeks. Exclusion: Non-English speakers, psychiatric treatment, multiple pregnancies, or planned terminations.
Statistical methodology and analysis:	Non-parametric Wilcoxon Mann-Whitney rank sum test. Powered at 80% to detect difference in psychological outcomes. Sample size estimated based on expected variance in HADS scores.
STUDY TIMELINES	
Study Duration/length	1 year
Expected Start Date	April 2026
End of Study definition and anticipated date	Final follow-up of last enrolled participant.
Key Study milestones	IRAS submission, ethics approval, first participant enrolment, data collection completion.
STORAGE of SAMPLES	
Data collected / Storage	PIA Viewpoint Database (King's College Hospital). Anonymised data stored securely on NHS OneDrive.

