For the patients allocated to intervention, the clinician will then calculate their score but inputting the patient's data on to a excel spreadsheet which will calculate the patient miscarriage prediction score using the following equation:

$$Y = -2.382 + 0.052 \times \text{maternal age (years with decimals)} + 0.482 \text{ if Afro-Caribbean} - 0.341 \text{ if South Asian} + 0.393 \text{ if East Asian} - 0.073 \text{ if Mixed ethnic origin} + 0.213 \text{ if Parous} + 0.647 \text{ if Smoker} - 0.165 \text{ if Abdominal pain as indication of the scan} + 0.709 \text{ if Vaginal bleeding as indication of the scan} + 0.239 \text{ if previous miscarriage as indication of the scan} - 0.226 \text{ if previous ectopic pregnancy as indication of the scan} - 0.241 \times \text{CRL (mm)} - 0.036 \times \text{delta FHR (bpm)} - 0.178 \times \text{delta Gestational sac diameter (mm)} + 0.633 \times \text{delta Yolk sac diameter (mm)} - 0.005 \times (\text{CRL} \times \text{delta GSD}) + 0.038 \times (\text{CRL} \times \text{delta YSD}) - 0.003 (\text{delta FHR} \times \text{delta GSD}) + 0.104 \times (\text{delta GSD} \times \text{delta YSD})$$

The patients randomized to intervention will then receive their score on the same day and could choose to do so either face to face or over the telephone. The General Practitioner will be informed of the patient's participation in the study.

For both groups 7 days after their initial assessment a repeat HADS and PSWQ score will be performed. This will be sent to the patient as previously consented. The patient will be sent two questions about the acceptability of the

1. Did receiving the miscarriage prediction score help you feel more informed and prepared about your pregnancy outcome? *(Yes/No, with an optional text box for further explanation.)*
2. Would you recommend that other women in early pregnancy receive a miscarriage prediction score as part of their care? *(Yes/No, with an optional explanation.)*

The primary outcome will be the difference in HADS and PSWQ at 7 days between cases and controls.

A power calculation was conducted to determine the required sample size for assessing the psychological impact of providing an individual with their miscarriage prediction score at the time of assessment. Given the non-parametric nature of Hospital Anxiety and Depression (HADS) scores, the Wilcoxon Mann-Whitney rank sum test was chosen.

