The study was calculated to have 80% power and to detect a probability shift of 0.362 with a 0.05 two-sided significance level. We estimated a 75% acceptance level and 20% dropout rate. Based on these parameters, an initial required sample size was calculated to be 104 participants per group, giving a total of 208 participants. After the adjustments for dropout rates and consent rates, this would equate to 186 participants per group and a total of 372 participants.

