9 STATISTICAL METHODS

Sample Size Derivation:

The planned sample size was calculated to detect a clinically meaningful difference in psychological distress scores (HADS and PSWQ) between the intervention and control groups. Based on prior studies, a non-parametric Wilcoxon Mann-Whitney rank sum test was selected due to the expected distribution of psychological score data.

Calculation Method:

The study was powered at 80% to detect a probability shift of 0.362 with a two-sided significance level of 0.05. Accounting for a 75% consent rate and 20% attrition, the adjusted total sample size is 372 participants (186 per arm). Statistical support was provided by

internal collaborators, and calculations were cross-verified using standard power analysis tables.

Justification for Design and Analysis Plan:

A randomised controlled trial (RCT) design was selected to allow unbiased assessment of the psychological impact of providing a miscarriage prediction score. The use of validated psychometric tools (HADS and PSWQ) permits a robust and reproducible outcome assessment. Analysis will compare between-group changes in scores from baseline to 7 days post-assessment.

Baseline Data Summary:

Demographic and clinical data, including maternal age, ethnicity, parity, smoking status, and presenting symptoms, will be summarised at baseline using descriptive statistics. Comparability of groups at baseline will be assessed.

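### The base size of 104 per group does not follow from the stated inputs: a rank-sum test with 80% power, two-sided 0.05 and a probability of 0.362 needs 69 per group

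*Protocol*

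**What the plan says.** Section 4 (Study Design) settles the test first: because HADS scores are treated as non-parametric, "the Wilcoxon Mann-Whitney rank sum test was chosen". It then gives the design inputs as "80% power and to detect a probability shift of 0.362 with a 0.05 two-sided significance level", followed by the recruitment allowances: "We estimated a 75% acceptance level and 20% dropout rate". From these it reports that "an initial required sample size was calculated to be 104 participants per group, giving a total of 208 participants". Only after that does it apply the dropout and consent adjustments, which bring the size to 186 per group and 372 in total.

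Section 9 (Statistical Methods) repeats the inputs: "The study was powered at 80% to detect a probability shift of 0.362 with a two-sided significance level of 0.05". It gives the adjusted total of 372 but not the 104, and says the calculations were checked against standard power tables.

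The Study Summary describes the basis in other terms: "Sample size estimated based on expected variance in HADS scores". Neither section defines probability shift, names a formula or software, or gives a different alpha, an unequal allocation or a multiplicity adjustment.

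**The concern.** For a two-group rank-sum test with equal arms, the significance level, the power and the probability P(X<Y) together fix the sample size. The protocol states all three and also states the size, so the statement can be checked. On the usual reading of 0.362 the size comes out about one third smaller than the 104 given.

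If the figures do not fit together, a reader cannot tell which effect the trial was designed to detect. That matters for judging whether the target difference is clinically sensible, and for reading a null result. The 104 is also the base for the recruitment target of 372, so an error there carries into the number of women approached and enrolled.

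**Working it through.** **Inputs from the protocol (sections 4 and 9).** Wilcoxon Mann-Whitney test; two-sided alpha 0.05; power 80%; effect 0.362; two equal groups; stated base size 104 per group.

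**Assumption.** Probability shift means P(X<Y) = 0.362, the probability that a score in one arm is below a score in the other. This is the usual effect measure for this test, with null value 0.5. The distance from the null is 0.5 − 0.362 = 0.138.

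**Attempt to reproduce 104.** Noether's formula for 1:1 allocation:

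n per group = (z₀.₉₇₅ + z₀.₈₀)² / [6 (p − 0.5)²]

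= (1.960 + 0.842)² / (6 × 0.138²) = 7.849 / 0.1143 = 68.7, so **69 per group** (138 in total).

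The stated 104 is 104/69 = 1.51 times this. It is not reproduced.

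**What 104 per group delivers.**
- Power for 0.362: Φ(0.138 × √(6 × 104) − 1.960) = Φ(3.447 − 1.960) = **93.2%**.
- Probability detectable with 80% power: 0.5 − 2.802/√624 = **0.388**.
- Under a normal shift, the standardised difference is √2 × |z(P)|: about 0.50 SD for 0.362 and about 0.40 SD for 0.388.

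**Is the approximation to blame?**
- With the variance under the alternative for a normal shift, power is 81.1% at 69 and 94.0% at 104.
- Simulation of the rank-sum test with a normal shift (10,000 runs) gives 80.8% at 69 and 94.1% at 104.
- Rounding and bounding the scores to 0–42, so that ties occur (assumed mean 14, SD 7), gives about 81 to 82% at 69 and 94% at 104.
- With the largest variance possible under the alternative, 80 per group already gives 81.5%.

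**Other readings and settings for a rank-sum test.**

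| Reading or setting | n per group |
|---|---|
| P(X<Y) = 0.362, as stated | 69 |
| Literal shift of 0.362 from 0.5, so P = 0.862 | 10 |
| Standardised difference of 0.362 | 120 to 139 |
| One-sided 0.05 (not stated) | 55 |
| 90% power (not stated) | 92 |
| Alpha 0.025 for two endpoints (not stated) | 84 |

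The range of 120 to 139 is the t-test size of 120, either taken as it stands or divided by a rank-test efficiency of 0.955 or 0.864.

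**Routes that land near 104.** Each needs something the protocol does not state:
- the one-sample sign-test formula: 7.849 / (4 × 0.138²) = 103.04, so 104;
- two-sided alpha of 0.01: 102.2, so 103;
- the larger arm of a 2:1 allocation: 103.04;
- 69 already inflated for dropout and consent: 69 × 1.20 × 1.25 = 103.5, so 104.

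**The case against.** The strongest reply is that the key input is undefined. The protocol never says what probability shift means, so P(X<Y) = 0.362 is the reviewer's assumption. That is fair, and the figure of 69 depends on it. But the two obvious alternatives give about 10 and 120 to 139 per group, so the assumption does not create the mismatch.

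A second reply is that the error is harmless. If 80% is read as a minimum, 104 per group meets it with room to spare. If the 372 are women enrolled and 20% drop out, about 149 per arm remain (186 × 0.80 = 148.8), with about 98% power for 0.362. This stands as to harm: type I error and the validity of the comparison are untouched. It does not rescue the statement, because section 4 presents 104 as the size required by these inputs.

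Three stronger readings are tempting, and the protocol does not support them.

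- A reader might infer that 104 cannot be reached by any route. It can, as the list above shows. What holds is narrower: none of the rank-sum calculations tried on the stated alpha, power and equal allocation gives 104.
- A reader might infer that dropout and consent were counted twice, since 69 × 1.20 × 1.25 = 103.5 and section 4 mentions both rates just before the 104. But the same section calls the 104 the initial figure and applies the adjustments afterwards. The one-sample formula fits as well. Double counting is possible and cannot be confirmed.
- A reader might infer that the Study Summary's reference to variance contradicts a rank-sum calculation. Noether's formula uses no SD, but the 0.362 may itself have been derived from an expected HADS difference and SD. The wording is not shown to be wrong and need not be deleted.

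**Conclusion.** The point holds as a mismatch between stated inputs and stated size. Assuming P(X<Y) = 0.362 and 1:1 allocation, the inputs need 69 per group, and the stated 104 is about 51% higher. Equivalently, 104 per group gives about 93% power for 0.362, or 80% power for about 0.388.

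Either the 0.362 or the 104 may be the wrong figure. If about 0.388 was intended, 104 is right. The protocol does not settle which.

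The error is conservative, and nothing here suggests an underpowered or invalid trial. The consequences are an unclear target effect (about 0.40 SD or 0.50 SD under normality) and possible over-recruitment. It should be fixed, but it is not a reason to hold up the trial.

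**What to change.** Define probability shift, name the formula or software, and restate one consistent set of figures in sections 4 and 9.

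- **Simplest option.** Keep 104 evaluable per arm and state 80% power for P(X<Y) of about 0.388 (about 0.40 SD under normality), with about 93% power for 0.362. For this point the cost is wording only.
- **If 0.362 and 80% power are the intended inputs.** State 69 evaluable per arm and re-derive 372 wherever it appears: the Study Summary and sections 4, 8 and 9. With 20% dropout alone, 69/0.80 = 86.25, so 87 per arm (174 in total). Dividing also by the 75% consent rate gives 69/(0.80 × 0.75) = 115 per arm (230 in total). This changes the recruitment target, so it is more than wording, but it needs no extra participants.

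In either case the sponsor should check the original calculation to see whether the 104 already contained the dropout and consent allowances. If it did, those allowances must not be applied again.

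The step from 104 to 186 is a separate matter and needs its own check: 104/(0.80 × 0.75) = 173.3, not 186.

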8 RECRUITMENT

Eligible participants will be recruited from the Early Pregnancy and Acute Gynaecology Unit at King's College Hospital. Recruitment will occur during routine clinical appointments for women undergoing early pregnancy ultrasound scans.

Recruitment Schedule:

Recruitment is planned to begin in April 2026 and will continue over a 12 month period until the required sample size of 372 participants is achieved.

Identification and Approach:

Patients presenting with a single live intrauterine pregnancy at less than 12 weeks' gestation will be identified by the clinical team as part of routine care. A delegated member of the research team will approach eligible patients after their clinical scan, explain the study, and provide the Participant Information Sheet (PIS).

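### The step from 104 to 186 per group does not follow from 75% consent and 20% dropout, and a pre-randomisation consent rate is built into the per-arm target

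*Protocol*

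**What the plan says.** Section 4 (Study Design) chooses the rank sum test: "the Wilcoxon Mann-Whitney rank sum test was chosen". It sets 80% power to "detect a probability shift of 0.362 with a 0.05 two-sided significance level" and arrives at 104 per group, 208 in total. It then assumes 75% acceptance and 20% dropout and states: "After the adjustments for dropout rates and consent rates, this would equate to 186 participants per group and a total of 372 participants".

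The same target appears in three other places:

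- Section 9 (Statistical Methods): "Accounting for a 75% consent rate and 20% attrition, the adjusted total sample size is 372 participants (186 per arm". It adds that the calculations were checked against standard power tables.
- Study Summary, target sample size: "372 participants (186 per arm, adjusted for consent/dropout".
- Section 8 (Recruitment): enrolment runs "until the required sample size of 372 participants is achieved".

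Section 5 (Study Schedule) lists the Day 0 steps and puts written consent before randomisation.

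**The concern.** Two things look wrong, and they are independent of each other.

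First, 186 is not what the two stated rates produce from 104.

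Second, a woman who declines consent is never allocated to an arm. Refusal is a loss between approach and randomisation; dropout is a loss between randomisation and the day 7 questionnaire. Only dropout belongs in a per-arm number. The protocol combines both and presents the result as participants per arm and as the point at which recruitment ends.

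What is at stake is the enrolment target. Staff cannot tell from the text whether 372 counts women approached or women randomised, and the two readings lead to very different trials. Section 15.3 also allows the study to stop if recruitment falls well short of expectation, so that judgement depends on the same figure.

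**Working it through.** **Inputs (section 4, repeated in section 9 except for the 104).** Evaluable number 104 per group, 208 in total; consent 75%; dropout 20%, so 80% retained. Stated result: 186 per group, 372 in total.

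**Step 1: try to reproduce 186.** Applying the two losses in sequence:

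- 104/(0.75 × 0.80) = 104/0.60 = 173.3, so 174 per group and 348 in total.
- Rounding once on the total: 208/0.60 = 346.7, so 347.
- Gap to the stated total: 372 − 348 = 24, or 372 − 347 = 25, about 7%. This is more than rounding.

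Other ways of combining the stated rates, per group:

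| Calculation | Result |
|---|---|
| 104 × 1.20/0.75 | 166.4, so 167 |
| 104 × 1.25/0.80 | 162.5, so 163 |
| 104 × 1.20 × 1.25 | 156 |
| 104 × 1.45 | 150.8, so 151 |
| 104/(1 − 0.45), losses added | 189.1, so 190 |

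None gives 186. Adding the losses comes closest, but it is not valid, because dropout applies only to women who consented.

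**Step 2: what 186 would imply.** 104/186 = 55.9% overall retention, against 0.75 × 0.80 = 60%. Two calculations with other rates do reach 186: 104/(0.70 × 0.80) = 185.7, and a 25% loss taken twice with rounding between (104/0.75 = 138.7, so 139; 139/0.75 = 185.3). Neither uses the stated pair of rates.

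**Step 3: put each loss where it occurs, taking 104 as given.**

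- Randomised: 104/0.80 = 130 per arm, 260 in total.
- Approached: 260/0.75 = 346.7, about 347.

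**Step 4: if 372 are randomised, as the per-arm wording says.**

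- Excess: 372 − 260 = 112; 112/260 = 43%. About half of these, 56, would be in the arm that receives the score.
- Evaluable: 372 × 0.80 = 297.6, about 298, or 149 per arm.
- Approached: 372/0.75 = 496.
- Power: if 104 per arm gives 80%, the standardised effect is 1.960 + 0.842 = 2.802 at that size. It grows with the square root of n: 2.802 × √(148.8/104) = 3.351. Then 3.351 − 1.960 = 1.391, which is a power of about 92%.

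**Step 5: if 372 are approached.**

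- Randomised: 372 × 0.75 = 279.
- Evaluable: 279 × 0.80 = 223, against 208 needed.

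**The case against.** The strongest reply is that nothing is lost. If 372 are randomised, the trial has more power than planned. If 372 are approached, about 223 women are evaluable, some 7% above the 208 required. Neither reading leaves the trial short of its own requirement, and neither biases the comparison between arms. That stands, and it limits the consequence. It does not make the figure right: under the first reading the target exceeds what the inputs call for by 43%; under the second, the per-arm number and the recruitment end-point are mislabelled.

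Four stronger readings are tempting, and the document does not support them.

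- *Power is 98%, not 80%.* A reader might take 0.362 as the probability that a score in one arm exceeds a score in the other and apply Noether's formula, which gives 98.5% at 149 per arm. On that reading 104 per arm already gives about 93%, and 69 per arm would give 80%. Setting 98% against 80% therefore mixes two baselines, and most of the rise belongs to the derivation of 104, not to the inflation. The protocol ties its 80% to 104 per group; from that baseline the figure is about 92%.
- *The authors used 70% consent.* That does reproduce 186, but so does a 25% loss taken twice. The source cannot be identified.
- *A further 112 women would be given the score.* Controls do not receive it, so the number is about 56. The protocol describes the model as developed on 5,427 pregnancies with prospective validation still to come.
- *The right target is 260.* This holds only if 104 holds, and 104 was not reproduced. If 0.362 is the probability above, 69 evaluable per arm are needed; if it is a standardised difference, 120, or about 126 allowing for the efficiency of the rank test. At 20% dropout, that range of 69 to 126 means 87 to 158 randomised per arm.

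**Conclusion.** The point holds on both counts. With 75% consent and 20% dropout, 104 per group inflates to 174 (347 to 348 in total), not 186 (372). In addition, the consent rate should not enter a per-arm number at all, because consent comes before randomisation.

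Assuming 104 evaluable per arm is correct and the two rates are as stated, 260 women should be randomised and about 347 approached. The document's inputs yield 372 for neither quantity. The per-arm wording makes 372 a number randomised, and so an over-recruitment of 112. The consequence is unnecessary enrolment and an unclear end-point for recruitment, not loss of power or a biased result.

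**What to change.** In the Study Summary and sections 4, 8 and 9, replace the single figure with three labelled numbers and show the arithmetic:

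- evaluable: 104 per arm, if that figure stands;
- randomised = evaluable/0.80: 130 per arm, 260 in total;
- approached = randomised/0.75: about 347.

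Section 8 should say which of these ends recruitment; it should be the number randomised. The derivation of 104 should be confirmed first, since the other two numbers scale with it.

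Alternatively, keep 372 as the number randomised, remove the consent adjustment from its justification, state the power it delivers (about 92% if 104 per arm gives 80%), and plan to approach about 496 women in the 12 months.

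The work is a few lines of text and no new data. The cost is a protocol amendment to the stated target and its justification, in a study that needs HRA and REC approval.

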5 STUDY SCHEDULE

Screening (Day 0)

- Record demographics and ultrasound findings in the Viewpoint clinical records
- 2D transvaginal ultrasound scan
- Verify eligibility based on inclusion/exclusion criteria.
- Provide information leaflet and verbal explanations
- Obtain and document consent from potential participant on screening consent form.
- Allocate a study number and record the patient's MRN / NHS number in the site file (paper)
- Use of the prediction model to calculate risk of miscarriage (study excel spreadsheet on NHS Onedrive)
- Randomisation into intervention or control group. If intervention, to be given miscarriage prediction score.
- Patients to complete HADS and PSWQ score
- Consent patient how they would like to be contacted for follow up

Repeat testing (Day 7)

- 7 days after initial assessment the patient will be sent follow up HADS, PSWQ score and acceptability questions.
- If patient does not complete score on this day, a reminder will be sent as per patients contact requests.

Table 1: Schedule of Assessments

	Screening	7 Days
Visit No	1	2
Window of flexibility for timing of visits:	+/- 2 days	+/- 2 days
Informed Consent	X	
Medical History	X	
2D TVUS	X	
Eligibility confirmation	X	
HADS/PSWQ Score	X	X
Acceptability Questions		X
Randomisation	X	
Adverse Events Review		X

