4 STUDY DESIGN

Study design

The Null Hypothesis:

Providing individuals with their miscarriage prediction score at the time of assessment has no significant impact on psychological distress, including anxiety, depression (HADS), and worry (PSWQ), compared to those who do not receive their score.

This is a prospective, two-arm, non blinded randomised controlled trial. It is a single-centre study taking place at King's College Hospital, Early Pregnancy Unit.

We will apply to the NHS Research Ethics committee and all the participants will be asked to give written consent.

Methods:

The inclusion criteria for this study include a singleton correctly sited intrauterine pregnancy with a visible fetal heartbeat less than 12 weeks gestational age. The patient should be over the age of 16. Exclusion criteria include multiple pregnancy, patients who intend to terminate their pregnancy, , patients who are being investigated or treated for a psychiatric condition or those who are non-English speaking.

Eligible patients who consent to take part in the study will be given an information leaflet and verbal explanation of the study.

At their appointment, the patients' demographic details, clinical history, ultrasound measurement and images will be documented on a computer database (PIA Foetal Database, Viewpoint Bildverarbeitung GmbH, Munich, Germany). For the purpose of this study the clinical data collected will include: maternal age, ethnicity, smoking status during pregnancy, parity and indication of presentation.

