A transvaginal ultrasound scan will be performed by a Gynaecologists who is specifically trained in early pregnancy ultrasound. The purpose of the transvaginal ultrasound scan includes determining the location of pregnancy, the viability and where appropriate recording of number of embryos. This is done with measurement of CRL, FHR, GSD and YSD. Pregnancy dating is based on CRL of a live embryo. In pregnancies < 7 weeks the greatest length of the embryo is taken as the CRL as crown and rump are not clearly visualised. Beyond 7 weeks, the CRL is measured in sagittal section of the embryo whilst excluding the yolk sac. The fetal heart rate is calculated as beats per minute using the software of the ultrasound machine after measurement with electronic calipers of the distance between two heart waves on a frozen M-mode image. The GSD is calculated as the average of three perpendicular diameter with the calipers placed at the inner edges of the trophoblast. The YSD is calculated as the average of three perpendicular diameter with the calipers placed at the center of the yolk sac wall. This is all part of routine clinical care.

At the end of their appointment, participants will be asked to complete a baseline HADs score. The HADs score is a widely used screening tool used to assess psychological distress, including anxiety and depression in clinic settings. It is a self-rating patient reported outcome measure. Fourteen items are divided equally in two subscales for anxiety (HADS-A) and for depression (HADS-B). The ratings of the 14 items are summed to give a final score ranging from 0 to 42. The HADs score has been used frequently in pregnant populations.

The PSWQ is a 16-item self-report scale which is designed to measure the trait of worry in adults.

The patients will be asked how they would like to be contacted in 7 days to repeat the HADS and PSWQ score. We will enquire if they consent to being contacted via email, telephone or text message.

Women will be randomly allocated to either receive their miscarriage prediction score or to the control group who do not receive any intervention. Randomisation will be carried out by the means of a computer-generated random numbers. To prevent selection bias, allocation will be concealed, and a secure online system (REDCap) will assign patients automatically.

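### The Day 0 schedule lists the HADS and PSWQ after randomisation and disclosure of the score, contrary to section 4; if followed, it would bias the change-from-baseline contrast in section 9.

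*Protocol*

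**What the plan says.** Protocol section 5 (Study Schedule) sets out Day 0 as ten bullets. The eighth is "Randomisation into intervention or control group. If intervention, to be given miscarriage prediction score". The ninth is "Patients to complete HADS and PSWQ score". It is the only Day 0 entry for either questionnaire, so it must be the baseline.

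Section 4 (Study Design) tells it in another order. It says "At the end of their appointment, participants will be asked to complete a baseline HADs score", describes the PSWQ, and asks how the woman wishes to be contacted for the repeat of both instruments. Next comes "Women will be randomly allocated to either receive their miscarriage prediction score or to the control group who do not receive any intervention". Calculation of the score follows, and then "The patients randomized to intervention will then receive their score on the same day and could choose to do so either face to face or" by telephone.

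Table 1 marks HADS/PSWQ and randomisation in the same screening column and fixes no order within the visit.

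On the use of the baseline, section 9 (Statistical Methods) states: "Analysis will compare between-group changes in scores from baseline to 7 days post-assessment". Section 4 defines the outcome differently: "The primary outcome will be the difference in HADS and PSWQ at 7 days between cases and controls". On blinding, section 4 states: "This is a prospective, two-arm, non blinded randomised controlled trial".

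**The concern.** A baseline serves a change analysis only if the intervention cannot have influenced it. Under the section 5 order, one arm completes the questionnaires after hearing its score and the other completes them without one. Whatever the score does at once to self-reported anxiety, depression or worry is then recorded as baseline in the intervention arm alone. Because the trial is open, knowing the allocation could itself shift the answers.

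The section 9 contrast would no longer measure the effect of disclosure to day 7. It would measure the difference between the day-7 effect and the immediate effect. No later analysis plan can repair this, since it cannot alter when a questionnaire was filled in. Mixed practice, with some staff following section 4 and others section 5, would leave baselines with different meanings in one dataset.

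**Working it through.** **1. The two orders side by side**

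| Step | Section 5 list | Section 4 narrative |
|---|---|---|
| Score calculated | before randomisation | after allocation, intervention arm |
| Randomisation | before questionnaires | after questionnaires |
| Score disclosed | before questionnaires | after allocation, same day |
| HADS and PSWQ | after disclosure | before allocation |

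Section 4 places the questionnaire at the end of the appointment. That does not settle the order, because disclosure may also be face to face on the same day.

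**2. What the contrast estimates**

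Let D7 be the true between-arm effect at day 7 and D0 the between-arm effect already present when the Day 0 questionnaire is completed.

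- Baseline before randomisation: D0 = 0 in expectation, so the change contrast estimates D7.
- Baseline after disclosure: the change contrast estimates D7 − D0.
- Unadjusted day-7 comparison: estimates D7 in either case.

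If D0 = f × D7, the change contrast is (1 − f) × D7. It shrinks for f between 0 and 1 and is inflated for negative f. For example, D7 = 0.5 and D0 = −0.25 give 0.5 + 0.25 = 0.75.

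**3. Inputs for an illustration**

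- Probability shift 0.362, two-sided 0.05, 104 per group before inflation: sections 4 and 9.
- Under normality with equal SDs, d = √2 × Φ⁻¹(0.638) = 0.499, taken as 0.5 SD.
- Baseline/day-7 correlation r = 0.6: assumed.
- f: assumed.

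The protocol's own sample size was checked first because the illustration borrows from it. Noether's formula gives a total of (1.960 + 0.842)² / (3 × 0.138²) = 137.4, or 69 per group rather than 104. By the same formula, 104 per group has 93% power at 0.362 and 80% power at about 0.388. The stated pair therefore does not reproduce. That is a separate matter, and step 2 does not depend on it.

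**4. Power of the change-score contrast, normal approximation**

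SD of change = √(2(1 − r)) = √0.8 = 0.894. SE of the contrast = 0.894 × √(2/104) = 0.124. Power = Φ(contrast/SE − 1.96), plus a negligible opposite tail except when the contrast is 0.

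| Share f present at Day 0 | Expected contrast (SD) | Contrast/SE | Power |
|---|---|---|---|
| 0 | 0.50 | 4.03 | 98% |
| 0.5 | 0.25 | 2.02 | 52% |
| 1 | 0 | 0 | 5% |

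**5. Sensitivity, simulated Mann-Whitney power on change scores, 104 per arm**

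| Effect | r | f = 0 | f = 0.25 | f = 0.5 | f = 0.75 | f = 1 |
|---|---|---|---|---|---|---|
| 0.362 | 0.5 | 94% | 76% | 43% | 14% | 5% |
| 0.362 | 0.7 | >99% | 93% | 63% | 21% | 5% |
| 0.388 | 0.5 | 82% | 57% | 30% | 11% | 5% |

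The simulated power of the unadjusted day-7 comparison is 94% at 0.362 and 82% at 0.388, whatever the value of f.

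**The case against.** The strongest reply is that the primary outcome in section 4 is a day-7 difference, with the Wilcoxon Mann-Whitney test named directly afterwards. That comparison does not use the baseline. This stands. A reader might infer that the trial's primary result is compromised, and the documents do not support that. The bias attaches to the change analysis in section 9, and the protocol states both without saying which governs.

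Second, the section 5 bullets are unnumbered and not strictly chronological: recording the ultrasound findings comes before the scan, and contact preference comes last although section 4 has it before allocation. The Study Summary and section 4 both speak of a baseline, which suggests a measure before intervention was intended. This is fair, and the conflict is best read as a drafting inconsistency, not a chosen design. But section 5 is the schedule staff would work from, and no statement elsewhere overrides it.

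Third, a reader might assume the trial hypothesises an immediate effect in the same direction as the day-7 effect. It does not. The null hypothesis in section 4 is of no impact and says nothing about when an effect would appear. An initial shock followed by reassurance would push the bias the other way.

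Fourth, a reader might take the two-day window in Table 1 to allow a baseline two days after disclosure. The row concerns the timing of visits, and everything on Day 0 belongs to one visit, so that reading is not supported.

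**Conclusion.** The contradiction is real: section 5 lists the only Day 0 questionnaires after disclosure, section 4 describes them before allocation, and no sentence fixes the order. If section 5 is followed, the section 9 contrast estimates the day-7 effect minus the Day 0 effect. That follows by algebra and requires no assumption about size.

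The size itself cannot be computed from the protocol, which gives neither the correlation nor any immediate effect. The fall from about 98% to 52% and 5% is illustrative. It rests on a 0.5 SD effect under normality (the protocol treats HADS as non-parametric), on r = 0.6, and on an immediate effect of the same sign as the day-7 effect. Other assumed values change the figures but not the pattern. With an immediate effect of opposite sign, the change score would overstate the day-7 effect instead. The unadjusted day-7 comparison is untouched throughout.

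**What to change.** - Reorder the Day 0 list in section 5 to match section 4.
- State in both sections that HADS and PSWQ are completed after consent and before randomisation and any disclosure of the score.
- Release the allocation only once completion is confirmed, for example by a tick-box in the REDCap randomisation form. Section 4 uses REDCap only for allocation and section 12 holds outcome data elsewhere, so a confirmation is enough; the questionnaires need not be captured in REDCap.
- Reconcile the day-7 outcome in section 4 with the change-score analysis in section 9, so that one is clearly primary.

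The cost is protocol wording and one confirmation field, with no extra visits. The correction should be in place before baselines are collected, because the timing cannot be recovered afterwards.
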